## 7.1 Dose Modifications

### Dose Modifications of Cabozantinib for Treatment-Related AEs

CTCAE v.5.0 Grade	Recommended Guidelines for Management a
Grade 1 AEs	Add supportive care as indicated. Continue cabozantinib treatment at the current dose level if AE is manageable and tolerable.
Grade 2 AEs which are tolerable and are easily managed	Continue cabozantinib treatment at the current dose level with supportive care.
Grade 2 AEs which are intolerable and cannot be adequately managed	At the discretion of the investigator, cabozantinib should be dose reduced or interrupted.  Note: It is recommended that dose holds be as brief as possible.
Grade 3 AEs (except clinically non-relevant laboratory abnormalities)	Cabozantinib should be interrupted unless the toxicity can be easily managed with a dose reduction and optimal medical care.  Note: It is recommended that dose holds be as brief as possible.
Grade 4 AEs (except clinically non-relevant laboratory abnormalities)	Subjects should have cabozantinib interrupted immediately. Discontinue cabozantinib unless the following criteria are met: 
 
• Subject is deriving clear clinical benefit as determined by the investigator and agreed by the Sponsor
 
• Toxicity can be managed with a dose reduction following recovery to Grade 1 (or baseline) and optimal medical care
 

AE, adverse event.

Note: The dose delay and modification criteria for specific medical conditions are provided below.

a Study treatment dose adjustment is only needed if the toxicity was deemed related to cabozantinib treatment or had an unclear relationship to cabozantinib treatment.

## Warnings and Precautions and Guidelines for the Management of Adverse Events

The most frequent adverse events experienced by  $\geq 20\%$  of subjects treated with cabozantinib were diarrhea, fatigue, nausea, decreased appetite, vomiting, weight decreased, PPES, constipation, hypertension, dysgeusia, dysphonia, and asthenia.

Adverse events associated with laboratory abnormalities experienced by  $\geq 5\%$  of subjects treated with cabozantinib include anemia, AST increased, ALT increased, hypothyroidism, hypokalemia, hypomagnesemia, thrombocytopenia, hypocalcemia, hypophosphatemia, lipase increased, lactate dehydrogenase (LDH) increased, neutropenia, ALP increased, hyponatremia, and leukopenia. Mild to moderate QTc interval prolongation (10-15ms) has also been observed with a QT interval calculated by the Fridericia formula (QTcF) not exceeding 500 ms.

Subjects may also experience medically important but less frequent adverse events including arterial and venous thrombotic AEs (eg, DVT, pulmonary embolism [PE], transient ischemic attack [TIA], and myocardial infarction [MI]), severe hemorrhagic events, proteinuria, wound healing complications, GI perforation, abscesses including intra-abdominal and pelvic abscess, GI and non-GI fistulae formation, osteonecrosis, and reverse posterior leukoencephalopathy syndrome (RPLS).

Cabozantinib treatment should be permanently discontinued for the following adverse events: visceral perforation or fistula formation, severe hemorrhage, serious arterial thromboembolic events, nephrotic syndrome, malignant hypertension, hypertensive emergency, persistent uncontrolled hypertension despite optimal medical management, osteonecrosis of the jaw (ONJ), and RPLS.

Guidelines for the management of AEs (ie, dose interruptions and dose reductions) are presented in the next sections. Each dose reduction of cabozantinib should be to one dose level lower than the current dose. Dose reductions of more than one dose level are acceptable per Investigator judgment. All AEs should also be managed with supportive care at the earliest signs of toxicity. Adverse reactions are presumed to be attributable to study drug. Adverse events classified as “not related” are defined as AEs that are, without question, not associated with the study treatment and definitely attributable to another cause.

The predicted effective plasma half-life of cabozantinib is 55 hours. Thus, when initiating therapy with cabozantinib, it will take most subjects 2 to 3 weeks to reach steady state. If AEs attributable to cabozantinib occur within the initial 3-week period of dosing, early intervention with dose modifications may be justified for AEs that, if worsened, could potentially be dangerous or debilitating, because without a dose adjustment, systemic exposure of cabozantinib might be expected to increase after the onset of the AE.

Events that generally have an early onset include hypocalcemia, hypokalemia, thrombocytopenia, hypertension, PPES, abdominal pain, mucosal inflammation, constipation, diarrhea and vomiting. In addition, earlier onset for events of dehydration was observed in subjects with CRPC when compared with subjects with other tumor types.

**Dose Modifications for Hematologic toxicity**

If a patient experiences dose-limiting Grade 4 neutropenia or thrombocytopenia, the treatment will be withheld. Counts should be checked every 3 - 4 days for thrombocytopenia and every other day for neutropenia during this time. If the toxicity resolves to meet eligibility parameters within 14 days of drug interruption, the patient may resume treatment at the next lower dose level. Doses reduced for toxicity will not be re-escalated, even if there is minimal or no toxicity with the reduced dose.

If dose-limiting toxicity does not resolve to meet eligibility or baseline parameters within 14 days of drug interruption, the patient must be removed from protocol therapy.

One dose reduction will be allowed for toxicity. If a patient does not tolerate reduced dose, they must be removed from protocol therapy.

**Dose Modifications for Non-Hematological toxicity**

If a patient experiences non-hematological dose-limiting toxicity as defined above, the treatment will be withheld. If the toxicity resolves to meet eligibility or baseline parameters within 14 days of drug discontinuation, the patient may resume treatment at the next lower dose level. Doses reduced for toxicity will not be re-escalated, even if there is minimal or no toxicity with the reduced dose.

The exception to this is Grade 3 weight loss as it is unlikely that the patient would return to baseline within 14 days. Patients who experience Grade 3 weight loss may resume study medication after a 14 day interruption with a dose-reduction if the patient is deriving benefit from therapy, and the treating physician feels it is in the best interest of the patient. If the weight loss does not recover within 6 weeks the patient must be removed from protocol therapy.

**Dose Modifications for Proteinuria**

Cabozantinib should be permanently discontinued in subjects who develop nephrotic syndrome (proteinuria > 3.5 grams per day in combination with hypoalbuminemia and peripheral edema [hyperlipidemia and thrombotic disease may also be present]) or any other relevant renal disease.

## Management of Treatment-emergent Proteinuria

[figure not shown]
Severity of Proteinuria (UPCR)	Management of Proteinuria
$\leq 1$ mg/mg ( $\leq 113.1$ mg/mmol)	
 
No change in cabozantinib treatment or monitoring
 

$> 1$ and $< 3.5$ mg/mg ( $> 113.1$ and $< 395.9$ mg/mmol)	
 
Consider confirming with a 24-hour protein assessment within 7 days
 
No change in cabozantinib treatment required if UPCR <math>\leq 2</math> mg/mg or urine protein <math>\leq 2</math> g/24 hours on 24-hour urine collection.
 
Dose reduce or interrupt cabozantinib treatment if UPCR <math>> 2</math> mg/mg on repeat UPCR testing or urine protein <math>> 2</math> g/24 hours on 24-hour urine collection. Continue cabozantinib on a reduced dose if UPCR decreases to <math>< 2</math> mg/mg. Consider holding cabozantinib treatment if UPCR remains <math>> 2</math> mg/mg despite a dose reduction until UPCR decreases to <math>< 2</math> mg/mg. Restart cabozantinib treatment at a reduced dose after a dose hold unless otherwise approved by sponsor.
 
Repeat UPCR within 7 days and once per week. If UPCR <math>< 1</math> mg/mg on 2 consecutive readings, UPCR monitoring can revert to protocol-specific times. (Second reading is confirmatory and can be done within 1 week of first reading.) If UPCR remains <math>> 1</math> mg/mg and <math>< 2</math> mg/mg for 1 month or is determined to be stable (<math>< 20\%</math> change) for 1 month, check urine protein/creatinine per protocol or as clinically indicated.
 

$\geq 3.5$ mg/mg ( $\geq 395.9$ mg/mmol)	
 
Hold cabozantinib treatment pending repeat UPCR within 7 days and/or 24-hour urine protein.
 
If <math>\geq 3.5</math> mg/mg on repeat UPCR, continue to hold cabozantinib treatment and check UPCR every 7 days. If UPCR decreases to <math>< 2</math> mg/mg, restart cabozantinib treatment at a reduced dose and monitoring of urine protein/creatinine should continue weekly until the UPCR decreases to <math>< 1</math> mg/mg. If UPCR remains <math>> 1</math> mg/mg and <math>< 2</math> mg/mg for 1 month or is determined to be stable (<math>< 20\%</math> change) for 1 month, check urine protein/creatinine per protocol or as clinically indicated.
 

Nephrotic syndrome	
 
Discontinue all study treatment
 

UPCR, urine protein/creatinine ratio.

## Dose Modifications for Hypertension

- Baseline blood pressure (BP) is defined as the blood pressure obtained at the examination used for study enrollment. This baseline BP should be obtained as follows:
  1. Obtain 3 serial blood pressures from the same extremity with the patient in the same position at rest with an appropriately sized cuff that are separated by at least 5 minutes. Avoid using the lower extremity if possible.
  2. Average the systolic blood pressure from the 2nd and 3rd measurements.
  3. Average the diastolic blood pressure from the 2nd and 3rd measurements.
  4. The baseline BP is the average of the systolic over the average of the diastolic measurements.
  
- Elevation in either the systolic or diastolic blood pressure should be considered when following the algorithm below.
- The upper limit of normal (ULN) is defined as a BP equal to the 95th percentile for age, height, and gender. See Appendix II.
- The NCI CTCAE 5.0 will be utilized to determine the grade of hypertension for reporting purposes.
- Elevated BP measurements should be repeated on the same day to confirm the elevation. If confirmed, patients with elevated BP should have BP measurements performed at least twice weekly until BP is  $\leq$  ULN.
- The algorithm^12 below will be used to manage cabozantinib-related hypertension.
- Hypertension should be managed with appropriate anti-hypertensive agent(s) as clinically indicated. It is strongly recommended that nephrology or cardiology be consulted in the evaluation and management of hypertension.

Elevations in BP are based on systolic or diastolic pressures.

† Elevated blood pressure (BP) measurements should be repeated on the same day to confirm the elevation. Patients with elevated BP at any time should have BP measurements performed at least twice weekly until BP is within the ULN.

§ ULN (Upper Limit of Normal) is a BP equal to the 95th percentile from age, height, and gender-appropriate normal values (Appendix VIII)

\* If BP > 25 mm Hg above ULN for age (verified) or Grade 4 HTN at any time, hold drug. Study drug should also be held for BP ≤ 25 mm Hg above the ULN age for > 14 days or 35 mmHg above baseline for > 14 days. Antihypertensive agents can be used to control hypertension as clinically indicated after study drug is held.

^ Anti-hypertensive therapy should be prescribed as clinically indicated, including the use of multiple anti-hypertensive agents.

# Baseline BP is defined in Section 6.4.

### Arm 1 of algorithm:

- If blood pressure (BP) ≤ 95% for age, height, and gender, continue cabozantinib at the same dose.

### Arm 2 of algorithm:

- If BP ≤ 10 mm Hg above the ULN for age, height, and gender, continue cabozantinib at the same dose and recheck the BP within 72 hours.
  - o If the BP is ≤ ULN on recheck, continue cabozantinib at the same dose.

o If the BP remains above the ULN on recheck, then start antihypertensive therapy and follow Arm 3 of the algorithm from the point that anti-hypertensive therapy is started.

### Arm 3 of algorithm:

- If BP is 11 to 25 mm Hg above the 95% for age, height, and gender on ≥ 2 of 3 measurements or > 35 mmHg above baseline on ≥ 2 of 3 measurements, start anti-hypertensive therapy, continue cabozantinib at the same dose, and monitor BP at least twice weekly.

- If the BP returns to  $\leq$  ULN within 14 days, continue cabozantinib at the same dose and continue anti-hypertensive therapy.
- If the BP remains elevated  $\leq$  25 mm Hg above the 95% or  $>$  35 mm Hg above baseline for more than 14 days after the institution of anti-hypertensive therapy, **hold** cabozantinib, monitor BP at least every 3 days, and follow Arm 4 of the algorithm from the point that cabozantinib is held. The antihypertensive therapy should be continued until the BP is less than the ULN.
  - If the BP returns to  $\leq$  ULN within 14 days of holding cabozantinib, restart cabozantinib at a reduced dose
  - If the BP remains  $>$  ULN for more than 14 days after holding cabozantinib, patient is off protocol therapy.
- If the BP increases to  $>$  25 mm Hg above the ULN despite anti-hypertensive therapy, **hold** cabozantinib, but continue the anti-hypertensive agent(s). Monitor the BP as clinically indicated and follow Arm 4 of the algorithm from the point that cabozantinib is held.
  - If the BP is  $\leq$  ULN within 14 days of holding cabozantinib, cabozantinib may be restarted at a reduced dose
  - If the BP is  $>$  ULN for  $>$  14 days after holding cabozantinib, the patient is off protocol therapy.

Arm 4 of algorithm:

- If BP is  $>$  25 mm Hg above the 95% for age, height, and gender, **hold** cabozantinib, monitor BP and administer anti-hypertensive therapy as clinically indicated.
  - If the BP returns to  $\leq$  ULN within 14 days of holding cabozantinib, cabozantinib may be restarted at a reduced dose
  - If the BP is  $>$  ULN for  $>$ 14 days after holding cabozantinib, the patient is off protocol therapy.

Arm 5 of algorithm:

- If the participant develops Grade 4 hypertension, discontinue cabozantinib, monitor BP and administer anti-hypertensive therapy as clinically indicated. The patient is off protocol therapy.

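### Arm 3 of the hypertension algorithm gives both a continue and a hold instruction when blood pressure falls to the ULN or below but stays more than 35 mm Hg above baseline

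*Combined protocol and SAP*

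**What the plan says.** Section 7.1, Dose Modifications for Hypertension, first sets the yardstick: "The upper limit of normal (ULN) is defined as a BP equal to the 95th percentile for age, height, and gender". The 95% limit in the arms is therefore the ULN. The arms then read as follows.

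- **Arm 1:** "If blood pressure (BP) ≤ 95% for age, height, and gender, continue cabozantinib at the same dose".
- **Arm 2:** "If BP ≤ 10 mm Hg above the ULN for age, height, and gender, continue cabozantinib at the same dose and recheck the BP", with 72 hours allowed for the recheck. A pressure that is then still above the ULN leads to antihypertensive therapy and Arm 3.
- **Arm 3, entry:** 11 to 25 mm Hg above the ULN or, with no reference to the ULN, "> 35 mmHg above baseline on ≥ 2 of 3 measurements, start anti-hypertensive therapy, continue cabozantinib at the same dose".
- **Arm 3, continue test:** pressure back at or below the "ULN within 14 days, continue cabozantinib at the same dose and continue anti-hypertensive therapy".
- **Arm 3, hold test:** still raised, by up to 25 mm Hg above the ULN or by more than "35 mm Hg above baseline for more than 14 days after the institution of anti-hypertensive therapy".
- **After a hold:** restart at a reduced dose if the pressure is at or below the ULN within 14 days; off protocol therapy if it is above the ULN for longer than that. Baseline is not mentioned.
- **Note to the algorithm:** the drug is also held for a lasting rise of up to 25 mm Hg above the ULN "or 35 mmHg above baseline for > 14 days".

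Section 4.2 gives two dose levels. It rules out re-escalation after a reduction and takes a subject with toxicity at level -1 off study.

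**The concern.** Arm 3 uses two yardsticks. Entry and hold can each be met on the rise from baseline, but every way out is judged on the ULN alone. The two agree for most patients. They disagree when baseline is low enough for a pressure to be acceptable against the ULN and still more than 35 mm Hg above where the patient started. For such a patient, adjacent bullets give opposite instructions on study drug, and nothing says which governs.

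At stake is a dose reduction that cannot be reversed and that brings the patient one step from removal. Two investigators following the text faithfully could manage the same patient differently. Safety and tolerability is a primary aim, and with 11 patients planned (Section 6) each patient is 1/11, or about 9 percentage points, of any tolerability proportion such as the share with a dose reduction.

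**Working it through.** The plan gives no figure to reproduce. The check applies the rules as written to one patient and then finds which baselines allow the conflict.

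**Inputs.** Systolic ULN is 136 mm Hg for a boy aged 17 or over at the 50th height percentile (Appendix II). Baseline 98 is an assumption: the documents give no baseline values, and eligibility sets only an upper limit. On treatment, the pressure falls from 150 to 135 within 14 days and stays there.

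**Step 1, entry.** 150 - 136 = 14 above the ULN and 150 - 98 = 52 above baseline. Both limbs of Arm 3 are met: antihypertensive therapy starts and cabozantinib continues.

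**Step 2, after 14 days at 135.** 135 - 136 = -1 against the ULN and 135 - 98 = 37 against baseline.

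| Test | Criterion | Met? | Instruction |
|---|---|---|---|
| Arm 3, continue | at or below ULN within 14 days | yes | same dose |
| Arm 3, hold | more than 35 above baseline for over 14 days | yes | hold |
| Note to the algorithm | 35 above baseline for over 14 days | yes | hold |

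The hold bullet is not conditional on the continue bullet having failed, so both apply.

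**Step 3, after a hold.** Restart at a reduced dose needs a pressure of 136 or less. At 135 that is met at once, although the 37 mm Hg rise that caused the hold is still present. The off-therapy test (above 136) cannot be met while the pressure stays at 135.

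**Step 4, which baselines.** A pressure P must satisfy P ≤ ULN and P > baseline + 35, so baseline < ULN - 35. In whole numbers, baseline ≤ ULN - 36. Systolic values at the 50th height percentile:

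- boy 17 or over: 136 - 36 = 100
- girl 17 or over: 129 - 36 = 93
- boy 10: 119 - 36 = 83
- boy 2: 106 - 36 = 70

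Either systolic or diastolic pressure can trigger an arm. For the boy of 17 or over, the diastolic figure is 87 - 36 = 51.

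**Step 5, the lesser overlap at entry.**

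- **Arm 1 and Arm 3:** the same baseline condition applies. With baseline 98, a first pressure of 135 (+37) fits Arm 1, which continues the drug and calls for nothing more, and Arm 3, which starts antihypertensive therapy.
- **Arm 2 and Arm 3:** P ≤ ULN + 10 and P > baseline + 35 give baseline < ULN - 25. With baseline 100, a pressure of 140 is 4 above the ULN and 40 above baseline. Arm 2 rechecks within 72 hours; Arm 3 starts therapy now.

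All three arms continue cabozantinib at this point, so the overlap affects only whether or when antihypertensive therapy starts.

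**The case against.** **The order of the arms may be shown elsewhere.** The symbols on the notes suggest a flow chart, which I have not seen, and it might rank the arms. That could settle the entry overlap. It would not remove the conflict between two adjacent written bullets in Arm 3.

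**The note may make the baseline limb an independent hold.** It supports that reading, since it repeats the hold with no ULN exception. But it does not say that it overrides the continue bullet.

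**The case is narrow.** This stands. A pressure that never exceeded the ULN cannot return to it, so for such a patient the continue bullet does not literally apply. The contradiction needs a pressure that rose above the ULN, came back, and stayed more than 35 mm Hg above baseline.

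**Two yardsticks may be intended.** Triggering on either criterion and recovering on the ULN could be a clinical choice. If so, the text still has to say what happens when the two disagree.

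A reader might also infer more than the documents support:

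- **A first reading that means both continue and hold.** At entry Arms 1, 2 and 3 all continue cabozantinib.
- **A sizeable affected share.** A normal model with an assumed SD of 8 to 12 mm Hg puts Phi(1.645 - 35/SD) = 0.3% to 10% of patients more than 35 mm Hg below the ULN at baseline, and Phi(1.645 - 25/SD) = 7% to 33% more than 25 below. These are assumed shares with a low baseline, not shares who meet the conflict. That also needs a rise of more than 35 mm Hg and, for the hold, persistence beyond 14 days on therapy.
- **A shift in the 6-month disease control rate.** No such effect is shown. Response is judged by RANO (Section 13), and adverse events are tabulated by CTCAE grade (Section 14.5) whichever arm is followed.
- **A limit of one reduction taken from the hematologic paragraph of Section 7.1.** That sentence sits under its own heading. The general source is Section 4.2.

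**Conclusion.** The contradiction within Arm 3 is real. For a pressure that exceeded the ULN, fell to it or below within 14 days on antihypertensive therapy, and stayed more than 35 mm Hg above baseline for more than 14 days, the text orders both continuation at the same dose and a hold. After a hold, restart at a reduced dose is available while the trigger persists. The overlap of Arm 3 with Arms 1 and 2 at entry is a lesser matter, because study drug continues in all three.

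The conflict needs a baseline more than 35 mm Hg below the ULN; the Arm 2 overlap needs one more than 25 below. The documents give no blood pressure distribution, so the frequency cannot be computed, and it is probably low. The worked example rests on the assumed baseline of 98. The point still deserves correction before use: the instructions on study drug are opposite, and the reduction at stake is not reversed.

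**What to change.** Reconcile Arms 1, 2 and 3 in Section 7.1 with the notes to the algorithm, and with any flow chart, so that a given blood pressure leads to one instruction. State which criterion governs when the ULN test and the above-baseline test disagree at three points: at entry, at day 14 of antihypertensive therapy, and after a hold. Align the note with Arm 3 on whether the rise is 35 or more than 35 mm Hg, since the two differ. Which rule and threshold apply, including whether recovery is judged on the ULN, on baseline or on both, is for the sponsor and investigators to decide.

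The cost is a wording change to Section 7.1 in a protocol amendment. Both baseline and on-study pressures are already collected, so no extra measurements are needed.

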### **Dose Modifications for Diarrhea**

If dose-limiting Grade 3 ( $> 3$  days) or Grade 4 therapy-associated diarrhea is experienced by a patient despite maximal use of anti-diarrheal medications, the dose of cabozantinib should be reduced. Loperamide should be used at the first sign of significant diarrhea.

Subjects should be instructed to notify their physician immediately at the first signs of poorly formed or loose stool or an increased frequency of bowel movements. Administration of antidiarrheal/antimotility agents is recommended at the first sign of diarrhea as initial management. Some subjects may require concomitant treatment with more than one antidiarrheal agent. When therapy with antidiarrheal agents does not control the diarrhea to tolerable levels, study treatment should be temporarily interrupted or dose reduced per table at beginning of section 7.1.

In addition, general supportive measures should be implemented including hydration, correction of fluid and electrolyte abnormalities, small frequent meals, and stopping lactose-containing products, high fat meals, and alcohol.

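### Four sets of hold, reduce and remove rules conflict in the current protocol, and no passage says which one governs

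*Combined protocol and SAP*

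**What the plan says.** **Grade 4 events in general.** The table that opens Section 7.1 covers treatment-related events. For Grade 4 it says "Subjects should have cabozantinib interrupted immediately. Discontinue cabozantinib unless the following criteria are met". The first criterion is "Subject is deriving clear clinical benefit as determined by the investigator and agreed by the Sponsor"; the second is that the toxicity can be managed by a reduction after recovery. A note under the table says that criteria for specific conditions follow.

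**Grade 4 diarrhea.** The diarrhea rule in 7.1 covers Grade 3 lasting more than 3 days: "or Grade 4 therapy-associated diarrhea is experienced by a patient despite maximal use of anti-diarrheal medications, the dose of cabozantinib should be reduced". Its next paragraph, on diarrhea that anti-diarrheal drugs do not control, says "study treatment should be temporarily interrupted or dose reduced per table at beginning of section 7.1".

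**Grade 4 hypertension.** The note to the hypertension algorithm puts BP more than 25 mm Hg above the upper limit of normal (ULN) in one clause with Grade 4: "or Grade 4 HTN at any time, hold drug". Arm 4, for the first of these, says that if BP returns to within "ULN within 14 days of holding cabozantinib, cabozantinib may be restarted at a reduced dose". Arm 5 says "If the participant develops Grade 4 hypertension, discontinue cabozantinib, monitor BP and administer anti-hypertensive therapy as clinically indicated" and places the patient off protocol therapy.

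**Number of reductions.** Section 4.2 has level 1 and level -1 only and takes toxicity at level -1 off study. Appendix VI has one reduced-dose column. The hematologic rule in 7.1 allows a single reduction. The Warnings and Precautions text in 7.1 accepts reductions spanning more than one level at the investigator's judgment. The proteinuria table provides for a hold when proteinuria persists despite a reduction, followed by restart at a reduced dose.

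**Anticoagulation.** Exclusion 2e in Section 5 admits patients on prophylactic heparin or LMWH. Section 7.2 (Thromboembolic Events) takes off study subjects who require anticoagulation, whatever the reason. Section 12(l) names only DVT that requires it.

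**The concern.** These rules decide whether a child with a severe event is held, reduced or removed. Where two current passages give different answers, two decisions that each comply with the protocol can differ, and a deviation cannot be judged cleanly. That is a patient-safety matter even at one site. It also touches the primary safety aim in Section 3, because reductions and removals are part of what tolerability means, and they will be hard to interpret if they partly reflect which passage was followed.

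**Working it through.** The check is a side-by-side reading. The plan states no figure on this point.

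**Set 1, Grade 4 diarrhea despite maximal anti-diarrheals.**
- Diarrhea rule: reduce. It states neither a hold nor a criterion.
- General Grade 4 row: interrupt immediately, then discontinue unless there is sponsor-agreed benefit and the event can be managed by a reduction after recovery.
- The two can end in the same place only when both criteria are met, and even then they differ on the immediate interruption. When a criterion is not met, one reduces and the other discontinues.
- The table's note points down to the specific rules without saying that they override it, and the diarrhea text points back up to the table. The cross-references form a loop.

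**Set 2, Grade 4 hypertension.**
- Algorithm note: hold, in one clause with a BP category that Arm 4 lets restart.
- Arm 5: discontinue, off protocol therapy.
- General Grade 4 row: a third version, with conditional continuation.
- The note and Arm 5 are both condition-specific, so preferring specific over general does not choose between them.
- The note and its companion footnote show other signs of unreconciled text. The note set cites an Appendix VIII, although the appendices end at VII and the BP norms are in Appendix II. Baseline BP is referred to a Section 6.4, although Section 6 has no subsections.

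**Set 3, number of reductions.**
- Levels below the starting dose: 1 (Section 4.2, Appendix VI).
- Reductions allowed by the hematologic rule: 1, then removal if the reduced dose is not tolerated.
- Levels one step may span under Warnings and Precautions: more than 1. From level 1 no such level exists.
- The proteinuria table can be read as keeping on treatment, after a hold, a patient in whom the only reduction has already failed. Section 4.2 takes toxicity at level -1 off study.

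**Set 4, anticoagulation.**
- At entry: prophylactic heparin or LMWH allowed.
- On study, Section 7.2 read literally: any need for anticoagulation means off study, with no exemption for prophylaxis allowed at entry.
- Section 12(l): only DVT that requires anticoagulation. Section 7.2 itself words the DVT condition two ways, once as anticoagulation being needed and once as possibly needed.

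**Smaller points.** Section 4.2 holds for toxicity until it falls to Grade 1, which implies Grade 2 or higher and makes no exception; the 7.1 table continues tolerable Grade 2 events at the current dose. The non-hematological rule relies on a definition of dose-limiting toxicity said to stand earlier in the text. Before it in 7.1, the term appears only for Grade 4 neutropenia and thrombocytopenia.

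**Scale.**
- Table 2-1, all causality, Grade 3 or higher: hypertension 330/2410 = 13.7%; diarrhoea 251/2410 = 10.4%. Both match the table. It gives no separate Grade 4 rate and no pediatric rate, so nothing is projected.
- Planned enrollment is 11 (Section 6). If all 11 are dosed, one patient classed as removed rather than reduced moves a discontinuation proportion by 1/11 = 9.1 percentage points. Section 14.5 names no such proportion; this shows only the weight of one patient.

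**The case against.** The best defence is that the text is less silent than it looks. The general table refers to condition-specific criteria, Section 4.2 refers to Section 7, and a footnote to the palmar-plantar erythrodysesthesia table leaves permitted dose levels to the individual protocol. This narrows the gap, but none of it states precedence, and the diarrhea rule refers back to the table.

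On the separate sets:
- **Hypertension.** A hold can be the immediate action and Arm 5 the final disposition. That reading is coherent but unstated. The note belongs to a figure not shown in the text available for this review, so its exact attachment cannot be checked. A reader might infer that the note lets Grade 4 patients restart; it does not say so, since restart comes from Arm 4. Nor does the permanent-discontinuation list contradict Arm 5 by naming "malignant hypertension, hypertensive emergency, persistent uncontrolled hypertension despite optimal medical management" and not Grade 4 as such, because the list is not said to be exhaustive.
- **Reductions.** The sentence in Warnings and Precautions concerns how far one step may go, not how many steps are allowed. That is fair, but it still permits a step for which no level exists. A reader might infer that the proteinuria table orders a second reduction. It speaks of a reduced dose, not a further reduced one, so this is only a possible reading.
- **Anticoagulation.** The sentence closes a paragraph on DVT and hemorrhage risk, so a therapeutic-only meaning is plausible. This is an ambiguity of scope, and the documents do not support saying that patients admitted on prophylaxis must be removed at once.

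Practical inconsistency is also limited: one program enrolls everyone, and Section 11 requires weekly meetings that review dose adjustments. That reduces divergence but does not tell the meeting which rule to apply.

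**Conclusion.** The concern holds for the four sets, with unequal strength. Diarrhea against the general Grade 4 row is a direct textual conflict. Hypertension and the number of reductions are unreconciled; the former has a compatible reading that the text does not state. Anticoagulation is the softest. The mismatch on tolerable Grade 2 events and the dangling pointer are drafting matters.

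The consequence is for patient safety and for consistent assessment of tolerability. The number of patients affected cannot be derived from the documents. A reader might go further and infer that the adverse-event incidences in Section 14.5 are distorted through time on drug. The documents do not establish this: the on-treatment period is not defined there, the safety analysis is descriptive, and all safety data are to be listed. Nor do they show that a general definition of dose-limiting toxicity is needed, since this single-arm pilot has no dose escalation; only the pointer is a defect.

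The conclusion rests on the current wording alone and takes no position on which clinical rule is right.

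**What to change.** Amend the protocol so that in each set one passage governs and the others refer to it:
1. The diarrhea rule and the general Grade 4 row in 7.1.
2. The hypertension note, Arms 4 and 5, and the general Grade 4 row, stating whether a hold is an interim step or the disposition.
3. Section 4.2, Appendix VI and the hematologic one-reduction rule with Warnings and Precautions and the proteinuria table.
4. Exclusion 2e, the Thromboembolic Events text in 7.2 and Section 12(l), stating how prophylaxis allowed at entry is treated on study.

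State the order of precedence among Section 4.2, the general 7.1 table and the condition-specific rules. Correct the pointer to a definition in the non-hematological rule. As a minor item, align the hold rule in 4.2 with the tolerable Grade 2 row.

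The investigator and sponsor decide which clinical rule applies. The cost is amendment wording only, with no change to sample size, data collection or analysis.
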